6.9 Unscheduled visit (when needed)

This type of visit can be performed at any time during the study, when the patient/study physician finds it necessary. For example, an unscheduled visit can be performed if the patient experiences discomfort at home due to ankle swelling that needs further investigation. In every unscheduled visit, the patient will undergo the following procedures:

- Physical examination
- Concomitant medications
- Document AEs
- Vital signs: (i) Resting supine BP, (ii) pulse measurement, (iii) temperature, (iv) pulse oximetry (incl. respiratory rate), and (v) weight

- ECG*
- Echocardiogram*
- Blood samples for haematology and clinical chemistry*
- Urinary pregnancy test (if indicated)

*if clinically required.

7. STUDY ASSESSMENTS

7.1 Physical examination, medical and medication history

Physical examinations will be performed to ensure suitability according to the inclusion and exclusion criteria at screening and to document the health status at the time-points specified in the Schedule of Events - see [Appendix 1](#). The physical examination (incl. vital signs) is a routine medical examination. A medical history will be recorded at screening only. The medical history will elicit information concerning existing medical conditions, major illnesses, and related surgical procedures. Any prescribed or over-the-counter medications that the subject received within the past 30 days should be recorded on the case report form (CRF). Medication prescribed for the treatment of PAH for 2 months prior to enrolment should be recorded on the CRF. Subjects will be instructed to notify the study physician before beginning new prescribed or over-the-counter medications.

7.2 WHO functional class

Functional assessment of PAH will be made according to the WHO classification system [\(26\)](#).

Class I:	Patients with PAH without limitation of physical activity. Ordinary physical activity does not cause increased dyspnoea or fatigue, chest pain, or near syncope.
Class II:	Patients with PAH resulting in slight limitation of physical activity. No discomfort at rest. Normal physical activity causes increased dyspnoea or fatigue, chest pain, or near syncope.
Class III:	Patients with PAH resulting in marked limitation of physical activity. There is no discomfort at rest. Less than ordinary activity causes increased dyspnoea or fatigue, chest pain, or near syncope.
Class IV:	Patients with PAH with inability to carry out any physical activity without discomfort. Indications of manifest right heart failure. Dyspnoea and/or fatigue may even be present at rest. Discomfort is increased by the least physical activity.

7.3 Vital signs

Systolic and diastolic systemic BP will be measured by means of either a standard manual or an automatic BP measuring device (cuff method). The same arm will be used for each measurement of BP, and BP will be measured after 5 minutes seated. Heart rate (HR), respiratory rate, and oxygen saturation will be measured by pulse oximetry after the subject has been at rest for at least 5 minutes.

7.4 Borg Dyspnoea Index

0	Nothing at all
0.5	Very, very slight (just noticeable)
1	Very slight
2	Slight
3	Moderate
4	Somewhat severe
5	Severe
6	

7	Very severe
8	
9	Very, very severe (almost maximal)
10	Maximal

7.5 Six-minute walk distance (6MWD):

Distance walked during an unencouraged 6MWT conducted according to American Thoracic Society guidelines (6). This is a standard tool for the study of functional capacity in PAH patients and is primarily determined by cardiac output and hence right ventricular function.

7.6 Laboratory measurements

7.6.1 Routine laboratory measurements

Routine clinical laboratory parameters (haematology, clinical chemistry) will be analysed by local accredited hospital laboratories. Tests may vary slightly depending on the availability of local hospital assays and so some flexibility with regards to the specific tests will be tolerated.

Routine laboratory tests include the following:

Haematology	White blood cell count (WBC) and differentials (neutrophils, lymphocytes, monocytes, eosinophils, and basophils), red blood cell count (RBC), platelet count, haemoglobin (Hb), haematocrit level (Hct), mean cell volume (MCV), mean cell haemoglobin level (MCH), mean cell haemoglobin concentration (MCHC), and reticulocytes, red cell distribution width (RDW)
Clinical chemistry	Albumin, total bilirubin, urea, creatinine, eGFR*, glucose, total protein, C reactive protein (CRP), urate, serum electrolytes [calcium (Ca), chloride (Cl), sodium (Na), phosphate (P), potassium (K), magnesium (Mg)], bicarbonate (HCO ₃), aspartate aminotransferase (AST), alanine aminotransferase (ALT), γ-glutamyl-transferase (γ-GT/gamma-GT), alkaline phosphatase (ALP), lactate dehydrogenase (LDH/LD), creatine kinase (CK), serum iron, thyroid stimulating hormone (TSH), free thyroxine (T4); also, brain natriuretic peptide (BNP) or N-terminal (NT)-pro hormone BNP (proNT-BNP)
Serum pregnancy test	beta human chorionic gonadotropin (β-hCG)

*eGFR using CKD-EPI will be calculated in ml/min per 1.73m² via the following weblink:

https://qxmd.com/calculate/calculator_251/egfr-using-ckd-epi

7.6.2 XBD173 assay

Plasma levels of XBD173 will be quantified by an external laboratory. Sample-related data (labelling information) will be pseudonymised (coded).

7.6.3 Genotyping

A sample at baseline will be taken for DNA extraction and analysed by polymerase chain reaction (PCR) using appropriate primers for single nucleotide polymorphisms (SNPs) related to TSPO activity. Sample-related data (labelling information) shared with Imperial College will be pseudonymised (coded).

7.6.4 Research blood samples

Blood samples will be collected for measuring biomarkers such as sVCAM1 and proNT-BNP and for future research studies. Research blood samples will be processed at the site of collection to extract plasma serum and cells, which will be stored locally in -80°C laboratory freezers. Frozen samples will be shipped to the central laboratory at Imperial College London (Pulmonary Hypertension Biobank), where they will be deposited for

future research focused on PAH and/or XBD173 studies. Data shared with Imperial College London to accompany research blood samples will be pseudonymised (coded). For selected measurements (e.g. proteomic analyses), samples or products of them shall be sent to accredited central laboratory/laboratories overseas (e.g. USA) contracted to perform proteomic analysis. Any data shared with these third parties will be anonymised. Details on preparation, labelling, storage and shipment of these samples can be found in the relevant section of the laboratory manual.

7.6.5 Volume of blood collection

The approximate blood volume collected from each individual during all scheduled visits is described in the table below. In addition, a further 4mL is required at screening for TSPO genotyping.

assessment	ml/collection	number of collections	total (ml)
haematology	3.0	4	12.0
clinical chemistry	10.0	4	40.0
serum pregnancy test	1.5	1	1.5
XBD173 assay	5.0	2	10.0
research blood	10.0	5	50.0
	total volume:		113.5 ml

7.8 Electrocardiogram (ECG)

A single 12-lead ECG will be conducted at baseline assessment, and at the following assessments on Weeks 4 and 8 (and at any unscheduled assessment, as needed). A qualified physician will be responsible for interpreting the ECGs. Any ECG finding that is judged by the site investigator as a clinically significant change (worsening) will be considered an Adverse Event.

7.9 Remote monitoring and management system of haemodynamic data

The CardioMEMS™ Heart Failure System (27) provides pulmonary artery hemodynamic data used for monitoring and management of Heart Failure patients. The system includes an implantable wireless sensor with delivery catheter, a remote monitoring electronics system, and a System database.

The wireless sensor is implanted into the distal pulmonary artery. Once implanted, the CardioMEMS Pulmonary Artery Sensor provides non-invasive hemodynamic data that is collected in the System database. The dataset includes details on the pulmonary artery pressure waveform, systolic, diastolic, and mean pulmonary artery pressure and cardiac rhythm (heart rate). This hemodynamic data is transferred online to a secure website that serves as the System database, so that monitoring information is available at all times.

8. ADVERSE EVENTS

8.1. DEFINITIONS

Adverse Event (AE): any untoward medical occurrence in a patient or clinical study subject.

Serious Adverse Event (SAE): any untoward medical occurrence or effect that:

- Results in death
- Is life-threatening – refers to an event in which the subject was at risk of death at the time of the event; it does not refer to an event which hypothetically might have caused death if it were more severe

- Requires hospitalisation, or prolongation of existing inpatients' hospitalisation
- Results in persistent or significant disability or incapacity
- Is a congenital anomaly or birth defect

Medical judgement should be exercised in deciding whether an AE is serious in other situations. Important AEs that are not immediately life-threatening or do not result in death or hospitalisation but may jeopardise the subject or may require intervention to prevent one of the other outcomes listed in the definition above, should also be considered serious.

8.2. REPORTING PROCEDURES

All adverse events should be reported. Depending on the nature of the event the reporting procedures below should be followed. Any questions concerning adverse event reporting should be directed to the Chief Investigator in the first instance.

8.3.1 Non serious AEs

All such events, whether expected or not, should be recorded

8.3.2 Serious AEs

An SAE form should be completed and emailed to the Chief Investigator within 24 hours. However, worsening of disease, death due to PAH, and hospitalisations for elective treatment of a pre-existing condition do not need reporting as SAEs.

All SAEs should be reported to the <name of REC> where in the opinion of the Chief Investigator, the event was:

- 'related', ie resulted from the administration of any of the research procedures; and
- 'unexpected', ie an event that is not listed in the protocol as an expected occurrence

Reports of related and unexpected SAEs should be submitted within 15 days of the Chief Investigator becoming aware of the event, using the NRES SAE form for non-IMP studies. The Chief Investigator must also notify the Sponsor of all related and unexpected SAEs.

Local investigators should report any SAEs as required by their Local Research Ethics Committee, Sponsor and/or Research & Development Office.

Contact details for reporting SAEs
[contact]
CI: [contact]
Please send SAE forms to:
[name]
[name]
[name]
[contact] (Mon to Fri 09.00 – 17.00)

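### Section 8.3.2 waives SAE reporting for disease worsening and PAH death with no exception for a suspected XBD173 effect, so such events can miss the 24-hour report and the only stated relatedness assessment

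*Protocol*

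**What the plan says.** Section 8.1 defines a serious adverse event by its outcome, whatever the cause; the first criterion is "Results in death". Section 8.2 opens with a general rule, "All adverse events should be reported", and then sends the reader to the procedures that follow it. For non-serious events, section 8.3.1 says "All such events, whether expected or not, should be recorded".

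For serious events, section 8.3.2 asks for a form to the Chief Investigator within 24 hours and then makes three exemptions: "However, worsening of disease, death due to PAH, and hospitalisations for elective treatment of a pre-existing condition do not need reporting as SAEs". SAEs go to the ethics committee, within 15 days, "where in the opinion of the Chief Investigator, the event was" both related and unexpected. The Sponsor step uses the same filter: "The Chief Investigator must also notify the Sponsor of all related and unexpected SAEs". A last clause covers local duties: "Local investigators should report any SAEs as required by their Local Research Ethics Committee, Sponsor and/or Research & Development Office".

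Section 11.6 lists drug-related serious events among the conditions for ending recruitment, without saying who decides that an event is drug-related.

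**The concern.** Exempting disease events from expedited reporting can be reasonable. The difficulty is that this exemption has no condition attached. It does not say what happens when the site suspects XBD173, when the worsening is unexpectedly severe, or who decides that an event is disease. Whoever applies the label at the site makes the causality decision in effect, and no one is assigned to check it.

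That matters more here than in many studies, for three reasons.

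- **Harm could look like disease.** XBD173 is used to alter endothelial function and, through it, pulmonary resistance (sections 1.1, 1.2 and 4.2). An adverse haemodynamic effect could present as worsening PAH.
- **There is no comparison group.** The study is open label and participants act as their own controls, so excess worsening cannot be seen against a control rate. Review of individual events is the main safeguard.
- **Prior experience offers little basis for excluding the drug.** The studies described in section 4.1 were in healthy volunteers and people with multiple sclerosis, and dosing lasted at most 7 days. None was in PAH. Section 1.2 mentions development to Phase IIa but gives no duration.

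At stake are prompt notice of a serious drug effect to the Chief Investigator, the ethics committee and the Sponsor, and the working of the recruitment stop in section 11.6.

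**Working it through.** The plan gives no figure to reproduce; the check is mainly of text.

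**1. Scope of the waiver.** There are three exempt categories. Elective hospitalisation for a pre-existing condition is not a concern. The other two, disease worsening and PAH death, are affected: 2 of 3. PAH death is worded by cause, so a site that suspects the drug might read the event as falling outside it. Disease worsening is not worded by cause at all.

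**2. What a waived event can miss.** In sequence: (a) the 24-hour form; (b) the Chief Investigator's view on relatedness, which section 8.3.2 attaches to SAEs; (c) the 15-day ethics committee report; (d) the Sponsor notification. Steps (c) and (d) arise only if (b) finds the event related and unexpected.

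**3. Whether another route replaces these steps.**

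| Route | Deadline to Chief Investigator | Relatedness judgement assigned |
|---|---|---|
| General AE rule (8.2) | none | none |
| AE checks at contacts and unscheduled visits (6.3 to 6.9) | none | none |
| Twice-weekly remote review, with coded data sent on request (4.1) | none | none |
| Grade 2 rules for the individual (4.1, 4.3.4) | none | none |
| Local-requirements clause (8.3.2) | none stated | none stated |
| Recruitment stop (11.6) | none | none |

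Result: 0 of 6 on both counts. Section 8.3.1 is not a seventh route, because it covers non-serious events only.

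**4. Timing.** The longest gaps between scheduled AE checks are Week 4 to Week 8 and Week 8 to Week 12: 4 × 7 = 28 days each, or 28 + 3 + 3 = 34 days at the edges of the ±3-day windows. Unscheduled visits can shorten this, but section 6.9 leaves them to judgement: "This type of visit can be performed at any time during the study, when the patient/study physician finds it necessary". The waived route asks for 24 hours.

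**5. Period concerned.** 8 weeks on drug + 4 weeks off = 12 weeks per participant; 6 × 12 = 72 participant-weeks, before replacements.

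**6. Exposure against the studies described in section 4.1.** Duration: 56 days / 7 days = 8 times the longest. Daily dose from the third participant onward: 180 mg / 90 mg = 2 times the highest. The second ratio assumes once-daily dosing in the 7-day study of 31 volunteers and 12 people with multiple sclerosis, where the frequency is not given.

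**7. Is a PAH death in this study remote? (Illustration only.)** Section 1.1 gives five-year mortality of about 58% for idiopathic or heritable PAH. Assume a constant hazard:

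- λ = −ln(1 − 0.58)/5 = 0.1735 per year.
- 8 weeks: p = 1 − exp(−0.1735 × 8/52) = 0.0263. Expected deaths 6p = 0.16; chance of at least one = 1 − (1 − p)^6 = 15%.
- 12 weeks: p = 0.0392. Expected deaths 0.24; chance of at least one = 21%.

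Participants must be clinically stable, so the true risk is probably lower. Worsening short of death is not counted. The figures show only that the waiver could come into use.

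**The case against.** The strongest reply is that the waiver is narrower than it looks and other safeguards surround it. The wording is permissive, so a site may still send a form. Waived events remain AEs to be reported under section 8.2, which also directs reporting questions to the Chief Investigator. Local bodies may set deadlines that the protocol does not reproduce. The Grade 2 rules act regardless of cause, and section 4.3.4 gives the Chief Investigator as well as the site the power to discontinue a participant. Starts are staggered by at least 2 weeks. The Sponsor or the Chief Investigator can stop the study on general safety grounds.

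All of this is true and lowers the consequence: such an event should not go unrecorded. It does not close the gap. Discretionary powers to stop work only on information that arrives, and a 2-week stagger protects the next participant only if a serious event is escalated within that time. Unseen local requirements cannot be counted on either way.

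Two further objections have force. Sections 4.2 and 10 attribute change during dosing to the drug, but they concern outcome measures, so the contrast with section 8.3.2 is an inconsistency of approach and not a contradiction. And section 8.3.2 ties relatedness to research procedures without naming the study drug, so restoring the 24-hour form would not by itself guarantee the later steps. The amendment should deal with that wording too.

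**Conclusion.** The concern holds. As written, section 8.3.2 allows a serious event labelled as PAH to bypass the 24-hour report and the only relatedness judgement in the protocol, and with them the ethics committee and Sponsor steps that depend on it. Two of the three exempt categories are affected, and none of the six other routes supplies a deadline to the Chief Investigator or a causality judgement.

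The conclusion rests on the protocol text alone; local reporting requirements and the separately filed Appendix 2 were not available. That drug harm would resemble PAH worsening is a plausible possibility, not a demonstrated effect: the haemodynamic evidence in section 1.2 is from animals and shows benefit. The protocol gives no rate of serious worsening or of misattribution, so missed events cannot be counted. This should be fixed because the repair is cheap and the study has few other means of detecting such harm.

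**What to change.** Amend section 8.3.2 so that any PAH worsening or PAH death meeting the section 8.1 criteria is sent to the Chief Investigator within 24 hours for a relatedness assessment. The rule should run from first dose to the end of follow-up: Week 12, or the 4-week call after early discontinuation in section 4.3.4.

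At minimum, state that the waiver does not apply where a relationship to XBD173 or a study procedure is suspected or cannot be excluded. This closes the stated gap but leaves the first attribution with the site.

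In either version:

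- name the study drug in the definition of relatedness;
- say whether PAH worsening and death count as expected events, since both are named in the protocol;
- keep the exemption for elective hospitalisation;
- bring sections 8.1 to 8.3.2 and 11.6 into line.

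The cost is a short amendment, which needs formal approval under section 11.5, and a few extra SAE forms and causality assessments in up to 6 participants plus replacements. The minimum version adds fewer. The exact number cannot be estimated from the protocol.

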9. DOCUMENTATION OF DATA

9.1 Data collection

The data collection tool for this study will be paper CRFs. Paper CRFs will contain study data which are verifiable to the source data (i.e., original recordings, laboratory reports, and subject records). In addition, all source data should be attributable (signed and dated). Only the site Investigator and authorised co-workers are entitled to make entries on the CRFs. Concomitant medications may be entered as they appear in the participant's record or as per local standards (generic or trade names may be entered). It is the responsibility of the site Investigator to ensure that the CRFs are kept up-to-date so that they always contain the latest observations on the subjects enrolled.

Pathology and imaging results outside the normal range will be identified and reviewed by the site Investigator. If they are deemed of clinical significance, they will be reported to the clinical care team. Other data than those requested by this protocol may be recorded as "additional data" in the comments section of the CRF; the clinical significance of any additional data should be described. Subjects' data will be stored in a validated database, developed and maintained by the Imperial College Trials Unit.

9.2 Data monitoring

The site Investigator is responsible for ensuring that the study is monitored appropriately in order to ensure compliance with GCP and local regulatory guidelines.

Data and all appropriate documentation will be stored for a minimum of 10 years after the completion of the study, including the follow-up period.

10. STATISTICS, SAMPLE SIZE AND DATA ANALYSIS

To maximize study efficiency, the design compares measures following treatment with those at baseline. The entry criteria will select patients that are clinically stable (No 6: no change in medication for over the preceding 1 month). It is assumed that any change in measures over the dosing period is a consequence of the intervention. While the study design is open label, the reliance on objective endpoints is intended to minimise bias in measurement and interpretation. This is a pilot study and therefore has not been formally powered. A 10% reduction in total pulmonary resistance would be of biological interest and will be related to change in endothelial markers.

Estimated frequencies and proportions will be summarized with descriptive analysis. Change in total pulmonary resistance and plasma levels will be presented as mean \pm standard deviations for continuous variables. The threshold for statistical significance will be established at 5%

[name] (CI) performed the statistical review of the study.

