The proposed study will recruit patients with PAH attending specialist clinics that have both an approved implanted cardiopulmonary monitor (CardioMEMS™ Heart Failure system) and an activity monitor (a Fitbit activity monitor) that permits remote sensing. The monitors will have been implanted on clinical grounds; specifically, to aid control of pulmonary hypertension by enabling more personalised dose adjustments to licensed treatments. Despite this, the drugs are not curative and patients live with very high pressures (typically 5 times normal resting pressures in a healthy individual). Patients with stable readings for at least a month will be considered for recruitment. These stable readings provide a good baseline from which to measure the effect of the study drug and relate to changes in blood biomarkers.

Remote sensing offers greater oversight of the patient and closer safety monitoring. Remotely acquired patient data are reviewed twice a week via a central clinical team based in Sheffield. Relevant data will be shared as de-identifiable information, and sent to Imperial College London (upon request) as pseudonymised (coded) data if there are any concerns regarding patients' safety. Follow-up would be scheduled by telephone or video conferencing with hospital visits being optional.

The most common side effects reported with XBD173 include nervous system and gastrointestinal symptoms, but the frequencies of these side effects are no higher than placebo.

If a patient is unable to continue with the prescribed dose of XBD173 to 8 weeks, they will be withdrawn from the study.

The end of the study will be the last visit of the last subject.

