4.2 Discussion of study design

This is an open label study. The aim of the study is to use XBD713 as a tool to modulate endothelial cell function, and to determine whether this is associated with a change in total pulmonary resistance (TPR). Patients with implanted devices act as their own control. A change in total pulmonary resistance from a stable baseline can be reasonably attributed to the study drug and would be expected to be accompanied by a reduction in plasma pro-NT-BNP. Patients will continue to be monitored at the end of the study, as part of clinical practice as the devices remain implanted, and any change in total pulmonary resistance return to baseline after discontinuing XBD173 will add weight to the interpretation.

No intervention or procedure which would normally be considered a part of routine care will be withheld.

[figure not shown]

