6.8 Assessment on Week 12 (Week 12 ± 3 days)

The patient will be invited to attend their local hospital or a home assessment will be made at the end of Week 12 in order to undergo the following procedures:

- Physical examination
- Concomitant medications
- Document AEs
- Vital signs: (i) Resting supine BP, (ii) pulse measurement, (iii) temperature, (iv) pulse oximetry (incl. respiratory rate), and (v) weight
- ECG
- Research blood sampling

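### Section 10 attributes any change over dosing to the drug, but no planned outcome or comparison uses the off-drug values that could help check this

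*Protocol*

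**What the plan says.** Section 10 of the protocol describes the comparison in these words: "the design compares measures following treatment with those at baseline". It then fixes how a difference is to be read: "It is assumed that any change in measures over the dosing period is a consequence of the intervention". Two supports are given there. One is unchanged medication for a month before entry. The other is that "the reliance on objective endpoints is intended to minimise bias in measurement and interpretation".

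Section 4.1 adds a further entry condition: "Patients with stable readings for at least a month will be considered for recruitment". Section 4.2 makes the control purely within-patient ("Patients with implanted devices act as their own control") and brings in the off-drug period: "any change in total pulmonary resistance return to baseline after discontinuing XBD173 will add weight to the interpretation". The same section leaves device monitoring after the study to clinical practice.

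Section 3.1 sets both primary measures at week 8. The exploratory measures in Section 3.3 are also changes from baseline. Treatment lasts 8 weeks and is followed by 4 weeks off drug (Section 4.1). The week-12 visit includes "Research blood sampling" (Section 6.8 and Appendix 1).

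**The concern.** Objective readings limit measurement bias. They do not stop the quantity itself from moving for reasons unrelated to the drug. With no concurrent control, a change from week 0 to week 8 mixes any drug effect with time trend, with regression to the mean and with effects of taking part. It also includes the effect of any other treatment given meanwhile. Section 11.3 allows clinicians to give alternative treatment and keeps those participants in the data analysis, so under the Section 10 rule a change caused by that treatment would also be credited to XBD173.

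Section 4.2 recognises the off-drug period as evidence on causation, but that reasoning does not reach the outcome list or the comparison. At stake is how a mean change in TPR or in a marker is interpreted. Non-drug movement could be read as a drug effect, or could hide one.

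**Working it through.** **Inputs from the protocol.** Up to 6 patients; measures at weeks 0, 8 and 12; drug stopped at week 8; a 10% TPR reduction is of interest; significance threshold 5%. The protocol gives no SD, no power and no drift, so there is no plan figure to reproduce. Drift and SD below are assumptions.

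**Size of a drift.** 0.5% × 8 weeks = 4%, and 1% × 8 = 8%, which is 40-80% of the 10% of interest. With no drug effect, a downward drift of this size would show as a 4-8% reduction. With a true 10-point reduction, an upward drift would leave an apparent reduction of only 6 to 2 points.

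**Illustrative chance of a significant result with no drug effect.** Assume a two-sided paired t test, n = 6, and a drift of 5 percentage points. Significance needs |mean|/SD ≥ 2.571/√6 = 1.05. The noncentrality is √6 × 5/SD:

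| Assumed SD of TPR change (points) | Chance of p < 0.05 |
|---|---|
| 5 | 51% |
| 10 | 17% |
| 15 | 10% |
| 20 | 8% |

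Without drift it is 5%.

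**What an off-drug value adds.** Write:
- E for the drug effect at week 8, and f for the fraction still present at week 12;
- D for a linear drift over 8 weeks, hence 1.5D at week 12;
- R for a one-off shift after baseline (regression to the mean);
- P for a participation effect confined to dosing.

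Then:
- Week 8 − week 0 = E + D + R + P
- Week 8 − week 12 = (1 − f)E − D/2 + P
- Week 8 − (1/3 week 0 + 2/3 week 12) is one third of the first plus two thirds of the second, which gives (1 − 2f/3)E + R/3 + P

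For D = 5 the drift terms are 5, −2.5 and 0. The weighted contrast removes linear drift, leaves one third of R and leaves all of P. The plain week 8 to week 12 change removes R but carries half the drift with opposite sign. If the effect persists in full (f = 1), the plain change shows none of E and the weighted contrast shows E/3.

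**Precision.** With independent errors of equal variance σ², the weighted contrast has variance (1 + 1/9 + 4/9)σ² = 1.556σ², so SD 1.25σ. Week 8 − week 0 has variance 2σ², so SD 1.41σ. Per unit of E, signal to noise is 1/1.41 = 0.71 for the plan's comparison. For the weighted contrast it is 1/1.25 = 0.80 with full washout and (1/3)/1.25 = 0.27 with full persistence. It can therefore support the main comparison but not replace it.

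**Availability of the data.** Week-12 research blood is scheduled. Section 4.3 describes daily device data, including pulmonary artery pressure and cardiac output. Recording of device readings, however, is listed only at baseline (Section 6.2). It is absent from Sections 6.7 and 6.8 and has no row in Appendix 1.

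**The case against.** The strongest reply is that detailed contrasts belong in a statistical analysis plan, which may exist. The assumption is openly declared, and Section 10 does not forbid use of week-12 data. This stands for the detail of the analysis. It does not cover the attribution sentence, which the protocol itself fixes and which a later plan would have to sit beside.

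The safeguards are also more than objective endpoints. Readings must be stable for at least a month. Section 4.3 describes the present cohort as stable over a mean follow-up of 7 months. Exclusion criterion 7 rules out a change of PAH therapy within 3 months before screening. The resistance threshold comes from an earlier catheterisation rather than the study baseline, which weakens the argument from regression to the mean. The exploratory analysis by rs6971 genotype offers a second, weak check. All this stands and lowers the risk. It does not remove it: the protocol puts no numerical limit on stable readings, and dosing lasts about twice the required stable month.

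A reader might infer that drift would inflate the drug effect. The documents do not support a direction. Section 1.1 says current treatments do not arrest or reverse the disease, so natural progression would tend to raise TPR and mask a reduction.

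A reader might also infer that the drift figures undermine the primary objective. That objective concerns the association between endothelial change and TPR change. A drift common to all patients shifts the mean changes but leaves their between-patient correlation unchanged. The figures above therefore bear on the mean change only.

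**Conclusion.** The point holds as a matter of interpretation and of unused information. The attribution sentence claims more than an uncontrolled before-after comparison can give, and the off-drug evidence valued in Section 4.2 is not carried into Sections 3 or 10. The 4-8% over 8 weeks is conditional on an assumed 0.5-1% per week in either direction; nothing in the protocol shows that such a drift exists.

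Two further inferences go too far. Sections 4.2 and 10 do not contradict each other: Section 10 omits the off-drug value but does not reject it. Nor should attribution depend on an off-drug return. No washout time is given, and Section 1.2 reports reduced vascular remodelling in animals, so an effect may last beyond 4 weeks. A missing return would be inconclusive, not evidence against the drug. This is an unpowered pilot, so a wording change and a modest supportive analysis are proportionate.

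**What to change.** 1. In Section 10, replace the assumption sentence with a stated limitation: change from baseline may reflect time trend, regression to the mean, co-treatment or participation as well as XBD173.
2. Add, for TPR and each marker, a supportive analysis that does not gate attribution: the week 8 to week 12 change, or week 8 minus (1/3 week 0 + 2/3 week 12). State what each leaves uncorrected, and that a missing off-drug return will be reported as inconclusive.
3. For TPR, show each patient's week-8 change against the variation in that patient's own device readings before dosing.
4. List recording of device readings at weeks 8 and 12 as well as baseline, in Sections 6.7 and 6.8 and in Appendix 1.

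No new visit or blood sample is needed. The cost is a little more analysis work and extraction of existing device data.
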